TITLE: Pain After Tonsillectomy (PAT) Study

SPONSOR: Alberta Children's Hospital Foundation

PRIMARY INVESTIGATOR: [name], R.Psych

CO-INVESTIGATORS: [name] FRCPC,
[name],
[name],
[name],
[name],
[name], PhD, FRCSC
[name],
[name],
[name]

BACKGROUND:

Pain is a common experience in childhood. Healthy children who are compliant with medical care undergo up to 20 painful procedures by the age of 5.¹ Moreover, millions of children undergo surgery (e.g., tonsillectomies) each year, which is commonly linked to pain and distress.² Pain from, and fear of, medical experiences are neither short lasting or benign and can influence children long after the painful stimulus is removed.³ Children's memories of needle-related, experimental, post-surgical, and procedural pain are a powerful predictor of future pain experiences, and are sometimes more influential to future pain than the initial experience of pain itself.⁴⁻⁶ Memory is susceptible to distortion. Negative biases in pain memories (i.e., recalling higher levels of pain as compared to initial pain report) are associated with higher subsequent pain, distress, and worse medical compliance.^{4,7} Empirical and theoretical work^{3,8} has implicated a number of factors in the development of negatively biased pain memories in children. Child sleep and language abilities have been shown to influence memory development following stressful and painful events.⁹⁻¹¹ Children who are more anxious and who experience greater pain are more likely to develop negatively biased pain memories,¹² which then leads to greater fear and pain at subsequent pain experiences.⁵ Parents and adolescents who think in more catastrophic ways about child pain prior to surgery tend to develop more negatively biased pain memories months later.¹³ In fact, parents' catastrophic thinking about child pain was found to be the single most important predictor of children's memory biases¹³ and subsequent pain trajectories.¹⁴ It has been suggested that parental and child anxiety lead to memory biases

Ethics ID: REB17-1794

Study Title: Pain After Tonsillectomy Study

PI: [name]

Version: 2

Date: December 4, 2017

Page 1 of 11

[figure not shown]

Figure 1. Cognitive and social developmental factors underlying the formation and expression of pain memories in childhood.

because of the ways in which parents and children talk about pain following painful events (e.g., by emphasizing threatening aspects of the experience).⁸

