One hundred children (50 intervention, 50 control) between the ages of 4-7 years and one of their parents will be recruited from the Ear Nose and Throat Clinic at Alberta Children's Hospital, where the PI's research laboratory is housed. A child will be eligible to participate in the proposed study if he/she 1.) is between 4 and 7 years old at the time of recruitment; 2.) is scheduled for an elective outpatient tonsillectomy (with or without adenoidectomy); 3.) is able to understand and speak English 4.) has at least one of his/her parents/caregivers consent to participating in the study and this caregiver is able to speak and read English.

Exclusion criteria include: 1) receiving pre-medication with anxiolytics (Midazolam; administered to < 5% of youth), as it might interfere with child's preoperative anxiety²¹ and memory formation;²² 2) serious medical co-morbidities (American Society of Anesthesiologists [ASA] \geq III physical status) that would interfere with standardized protocols of analgesic administration and surgical technique; 3) developmental disabilities or speech/language delays, as it may make it difficult for the participants to complete all necessary study tasks (e.g., assent, narrative task, memory interview).

Procedure

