the in-hospital and post-surgery periods. The intervention will draw from existing narrative-based interventions that have taught parents to reminisce with their children about past negative events in more elaborative and emotion-rich ways (e.g., using more open-ended questions, to follow up on children's answers by providing new details about the event, to talk more about emotions, and to praise children's answers). We will also include elements of past pain memory reframing interventions and findings from our recent data. Specifically, parents will be taught to reminisce with their children about the in-hospital and post-surgery periods by providing more explanations for events, using less utterances about pain, fear, and medical procedures, emphasizing positive aspects of the child's surgery memory (e.g., when children used coping methods such as deep breathing, when they got a treat),²⁵ and enhancing children's self-efficacy regarding their ability to cope with pain.²⁶ Similar to previous interventions, to boost mastery of the material, the researcher will use short videos of prototypical parent-child reminiscing about the in-hospital and post-surgery periods to illustrate adaptive and maladaptive reminiscing style and content. Researchers will also provide suggestions for specific questions and remarks to make while reminiscing. Parents and researchers will engage in brief role-plays to solidify the techniques, which will be followed by researcher feedback. After this training period, parents in the intervention group will be instructed to reminisce with their children about the in-hospital and post-surgery periods *using the intervention strategies*.

After parents have finished reminiscing about the in-hospital and post-surgery periods with their child, parents in both groups will be asked to complete a short questionnaire containing similar measures as completed at baseline.

Three to four weeks after surgery, children in both groups will complete a telephone pain memory interview to assess children's recall of the in-hospital and post-surgery periods.^{13,27} Then, parents in the intervention group will complete a brief semi-structured telephone interview to assess feasibility and acceptability of the intervention.^{19,28}

Incentives

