Memory. Three to four weeks following surgery, children will be asked to complete a pain memory interview via telephone that is based on a previously published protocol used with children aged 5-10 years following venipuncture.²⁷ Children will be asked to recall the in-hospital and post-surgery periods (i.e., while at home) time periods and complete the same pain intensity and pain-related fear scales based on their memories of those time periods. Biases in memory will be defined as the deviation in recalled and initial/experienced pain reports. Similar to our previous research, statistical models predicting pain memories will control for initial pain ratings that correspond to each memory question.^{4,9,10} Negatively biased pain memories will be defined as children who remember more pain and fear as compared to their initial pain reports. Positively biased pain memories will be defined as recalled pain that is less than initial pain reports. Accurate memories reflect no difference between recalled and experienced levels of pain.

Medical records review. Through the medical records review, we will gather information about the surgery technique, parental presence at induction, anesthetic technique (maintenance with volatile or TIVA), intraoperative opioid administration, awake or deep extubation, duration of PACU stay, pain scores using FPSR, analgesic administration, parental presence in PACU, analgesic administration in Day Surgery (and overnight stay if that applies), etc.

Analgesic consumption after discharge. Analgesic administration (or absence thereof) will be recorded after discharge on days 1, 2, 3, 7, and 14 at home. The questions will include medicine type (including any specific remedies to reduce pain due to swallowing), dose, and number of times medicine was administered.

Socio-demographic forms. A brief socio-demographic form will be administered to account for such variables as ethnic background, level of education, household income, and family composition.

Medical history questionnaire. A brief questionnaire will be administered to assess variables such as family surgical and medical history and surgery preparation and knowledge.

Statistical Analyses

A sample size of 52 children is required to detect medium effect sizes and exceeds the published recommendations for pilot interventions.⁴⁶ We will inflate the sample size to N=100 (50 per group) to account for attrition rates.

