Group differences in memory will be analyzed using analysis of covariance, while controlling for child age, sex, language ability, and initial pain ratings. Similar analyses will examine group differences in pain narratives to provide evidence of treatment fidelity. Feasibility and acceptability will be summarized using descriptive statistics. Hierarchical regression models will be used to examine the predictive value of child and parent characteristics on pain memories. Prior to consideration for inclusion in the models, variables will be subjected to multicollinearity diagnostics via assessment of variance inflation factors. Remaining candidate variables will be included in the models. Similar to previous research, semi-structured interviews will be conducted with parents to assess acceptability and satisfaction. Interviews will be analyzed using semantic thematic analysis conducted using NVivo software.¹⁹

TIMEFRAME

A 9-month timeframe is proposed for the completion of the present pilot study project: 7 months will be needed for continuous recruitment of participants. We aim to recruit 15 families per month. The final two months will be used to complete the last wave of memory interviews and data entry, run statistical analyses and prepare manuscripts for publication.

References

1. Public Health Agency of Canada. Canadian Immunization Guide. Public Health Agency of Canada; 2013.
4. von Baeyer CL, Marche TA, Rocha EM, Salmon K. Children's memory for pain: overview and implications for practice. *J Pain*. 2004;5(5):241-249.
7. Arntz A, van Eck M, Heijmans M. Predictions of dental pain: the fear of any expected evil, is worse than the evil itself. *Behav Res Ther*. 1990;28(1):29-41.

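### The efficacy ANCOVA leaves out baseline parent catastrophizing, the predictor of memory bias that the Background ranks first; adding it would gain precision and close one route to attrition bias.

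*Combined protocol and SAP*

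**What the plan says.** Statistical Analyses gives the efficacy model in one sentence: "Group differences in memory will be analyzed using analysis of covariance, while controlling for child age, sex, language ability, and initial pain ratings". The Background, citing earlier work, says that "parents' catastrophic thinking about child pain was found to be the single most important predictor of children's memory biases". Under Procedure, parents complete the catastrophizing measure one week before surgery, about three weeks before randomization at the 2-week lab visit. Parent characteristics enter the plan only through the hierarchical regressions, which serve the secondary aim.

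The outcome comes from a single contact, 3-4 weeks post-operatively, at which "children in both groups will complete a telephone pain memory interview to assess children's recall of the in-hospital and post-surgery periods". On numbers, the plan says "A sample size of 52 children is required to detect medium effect sizes" and then "We will inflate the sample size to N=100 (50 per group) to account for attrition rates". It gives no attrition rate, and it does not say how a child without a memory interview is analysed. Completion of study elements is listed only as a descriptive feasibility measure.

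**The concern.** A baseline variable that is strongly related to the outcome and measured before randomization is the natural covariate for an ANCOVA. It shrinks the residual variance at the price of one degree of freedom. Here such a variable is named in the plan, collected, and then left out of the one model that tests the intervention. In a trial with 26 to 50 analysed children per arm, the precision lost is worth having.

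There is a second consequence. With no rule for missing recall scores, the ANCOVA will in practice use completers. If more highly catastrophizing parents leave one arm but not the other between the lab visit and the interview, the remaining children differ between arms on a predictor that the model does not contain. Part of that difference would be read as an intervention effect.

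**Working it through.** **1. The plan's own figures.** The inflation is N = 52/(1 - a). With N = 100, a = 1 - 52/100 = 48%. For comparison, 20% attrition needs 52/0.80 = 65 children and 30% needs 52/0.70, rounded up to 75. So 48% is the most loss the target can absorb; the plan does not predict it. (The 52 itself cannot be rebuilt, because alpha, power and a numeric effect are not stated. At two-sided 5% and 80% power, d = 0.5 needs 128 in total and d = 0.8 needs 52. That is a separate matter.)

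**2. Which part of that loss can depend on arm.** The Sample section says "One hundred children (50 intervention, 50 control) between the ages of 4-7 years and one of their parents will be recruited", which happens before surgery. Randomization is at the 2-week visit and the interview at 3-4 weeks. Arm can influence loss only in the 1-2 weeks between them. Cancelled surgery, early withdrawal and a missed lab visit all come before allocation.

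**3. Precision.** The documents give no coefficients, so these are assumptions: recall SD 1, coefficient 0.4 for initial pain, coefficient r = 0.3 to 0.5 for PCS-P, standardized and mutually independent predictors, true effect 0.5 SD, two-sided 5%.

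- Residual variance without PCS-P: 1 - 0.4² = 0.84, SD 0.917, so the effect is 0.5/0.917 = 0.546 residual SDs.
- With PCS-P, r = 0.3: 0.84 - 0.09 = 0.75, SD 0.866, effect 0.577.
- With PCS-P, r = 0.5: 0.84 - 0.25 = 0.59, SD 0.768, effect 0.651.
- The standard error is multiplied by √(0.75/0.84) = 0.945 or √(0.59/0.84) = 0.838, a cut of about 5% to 16%.

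Simulated power, with loss unrelated to PCS-P:

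| Analysed per arm | Planned ANCOVA | With PCS-P (r = 0.3 to 0.5) |
|---|---|---|
| 40 (20% of 50 lost) | about 67% | 71-80% |
| 26 (48% of 50 lost) | about 47% | 52-61% |

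A closed-form noncentral-t check with noncentrality (effect in residual SDs) × √(n/2) gives 67% against 72-82% at n = 40, and 49% against 53-63% at n = 26. It runs up to about two points higher because it ignores chance imbalance in the covariates and in arm sizes.

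**4. Bias in a completers' analysis.** Simulation of 4,000 trials per setting, 50 per arm, true effect zero. Assumptions: coefficient 0.5 for initial pain and 0.4 for PCS-P; where loss depends on PCS-P, its log-odds rise by 1 per SD of PCS-P. A negative sign favours the intervention.

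| Loss after randomization | Dependence on PCS-P | Bias, planned model (SD) | Type I error |
|---|---|---|---|
| 60% intervention, 36% control | none | -0.01 | 5% |
| 48% in each arm | same in both arms | -0.01 | 4% |
| 10% in each arm | intervention arm only | -0.03 | 6% |
| 20% in each arm | intervention arm only | -0.07 | 6% |
| 48% in each arm | intervention arm only | -0.16 | 10% |

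With PCS-P in the model, the mean estimate stayed within 0.012 SD of zero and type I error was 4.6-5.2% throughout. That repair is built into the set-up, since loss was made to depend on nothing but arm and PCS-P.

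**The case against.** The case against has real force on the bias side.

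- A reader might infer that the plan expects 48% of randomized children to be lost. It does not: 48% is a ceiling on loss from recruitment to interview, and only the last 1-2 weeks are exposed to arm.
- A reader might infer that omitting PCS-P, or unequal loss between arms, biases the estimate in itself. Neither does. Randomization protects against the omission, and loss of 60% against 36% by arm alone gave -0.01 SD. Bias needs loss to relate to catastrophizing, or another outcome predictor, differently by arm.
- The design works against such loss. Both arms have a 20-minute researcher session, reminisce at the same visit, have the same telephone interview and receive the second gift card only after it. The extra parent interview in the intervention arm follows the memory interview.
- The Background sentence rests on one cited study, introduced in terms of parents and adolescents with recall months later. Here the children are 4-7 years old and recall is at 3-4 weeks. The strength of PCS-P in this trial is unknown, and the plan treats it as a secondary hypothesis.
- This is a pilot, and PCS-P is to be examined in the hierarchical regressions.

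The first four points stand and set the size of the claim. The last does not remove it: preliminary efficacy is part of the primary aim, with a directional between-group hypothesis, and the regressions answer a different question from the group comparison.

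**Conclusion.** The point holds as a low-cost improvement to the efficacy model. The gain is mainly in precision: roughly 4 to 13 percentage points of power with 40 per arm and 5 to 14 with 26 per arm, if the PCS-P coefficient is 0.3 to 0.5 SD. A weaker association would bring a smaller gain.

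The protection against selective loss is secondary and conditional. At 10-20% post-randomization loss, with dependence in one arm only, the bias at stake is small and type I error stays near 6%. The larger figure of -0.16 SD needs the entire 48% to fall after randomization, which the documents do not suggest. All coefficients and loss slopes are assumptions. The documents do not support saying that the planned estimate is biased, only that it could be under these conditions.

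Adding PCS-P would not repair loss that depends on the unobserved memory score itself, so a simple sensitivity analysis is still needed.

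**What to change.** 1. In Statistical Analyses, add the PCS-P score taken one week before surgery to the covariates of the memory ANCOVA. Specify that time point: parents complete measures similar to baseline again after the lab-visit session, and a post-intervention score must not be used as a covariate.
2. Report by arm how many randomized children have no memory interview.
3. Add one sensitivity analysis that assigns recall scores to children lost from the intervention arm and shifts them upward in steps until the conclusion changes.

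A fuller imputation by arm is not asked for; with perhaps 26 completers per arm its behaviour has not been checked.

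Cost: one degree of freedom, a sentence or two of text and a little analysis work. No new data, visits or participants are needed. Settle the wording before outcome data are seen.
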